8.0 Data Management and Information Security

8.1 Data Management

The UW DCC will host a public facing web page that provides a centralized location for information about the research project for patients, investigators, and institutional agencies. The public-facing web page contains a link to an https-secured web-based portal (<https://uwdcc.org/portal/cisto>) that provides a centralized location to securely perform study data management activities using individual Single Sign on (SSO) user names and passwords sponsored by the UW DCC.

The UW DCC supports an installation of REDCap (Research Electronic Data Capture: <http://www.projectredcap.org>), which is software specifically designed for electronic data capture in research studies. All data entered are site-specific and not available to personnel at other recruitment sites. Investigators with UW DCC research studies have the flexibility to collect data through mailed paper-based surveys, computer assisted phone-based interviews, SMS messages, or with web-based surveys. For most studies, we also provide customized statistical reporting and C#, .NET, and R programming beyond what REDCap provides natively. Data systems are interlinked through the REDCap application programming interface (API).

8.2 Information Security

All participant data collected on paper at sites will be stored in locked file cabinets located in the site research offices.

Electronic data captured under the CISTO protocol will be stored and accessible only through REDCap and will not be stored locally on laptops or tablets. Additionally, protected health identifiers will be stored in a REDCap database without data export rights enabled. Data stored on the University of Washington REDCap servers are only accessible to allowed study personnel through SSO authentication procedures. Many institutions that have installed REDCap have made use of enterprise-level web application security scanners, such as HP Webinspect and Acunetix, to scan and test REDCap's security and its ability to withstand various methods of attack. REDCap has performed very well in such instances.

Access to research data collected in each UW DCC study is restricted to study team members at each site and appropriate UW CCC and DCC personnel. Protected Health Information (PHI) from clinical recruitment sites are protected by virtual machine servers and stored in server room that meets the technical requirements for Health Insurance Portability and Accountability Act (HIPAA) compliance.

8.3 Subset of Patients and Caregivers

For the qualitative interviews obtained from a subset of patients and caregivers, only the research team will access the interview data, including transcripts and any field notes produced during interviews. Data will be kept in a password-protected database. Audio recordings may include identifying information (such as name or title), but these will be removed from the transcripts of those files and the original audio files will be destroyed. We will keep audio recordings until a transcript has been created and reviewed for accuracy. As is consistent with other approved research activities, all other records (e.g., transcripts, field notes) will be de-identified, and will not contain participant name or any other identifying information.

Presentations of findings, such as conference papers, will present most data in aggregate form. Qualitative feedback may be presented as participant quotes, and care will be taken by the research team to select generalized quotes that minimize disclosure of an individual participant by excluding names, locations, organizations, and other cues to participant identity.

9.0 Statistical Analysis Plan

9.1 Delineation of Treatment Arms

We will use block recruitment within practice sites, no more than two thirds of whom within each completed block may be medical management patients. Using block recruitment ensures that the study will be sufficiently well balanced to adequately characterize the effect of each treatment relative to the other and maintain power to evaluate primary and secondary outcomes. Each treatment arm is defined by each patient's choice of treatment at enrollment. If a patient ultimately receives a different treatment from what they chose initially, this is considered as an outcome of their initially chosen treatment. We expect that all or almost all patients who choose radical cystectomy will receive it prior to evaluation of the primary endpoint at 12 months post-enrollment, while up to 20% of patients who choose medical management may undergo radical cystectomy during this period.

9.2 Analytic Plan

We will use descriptive statistics to characterize the treatments received, clinical outcomes and PROs, and patient and caregiver participant preferences. We will compare continuous demographic and clinical characteristics by treatment group with nonparametric tests to protect against violations of normality assumptions. Exact p-values from Exact Conditional Tests, such as Fisher's exact test and its multi-degree of freedom extensions, will be used to compare categorical data.

Aim 1 hypotheses relate to the effect of the two treatments (radical cystectomy and medical management) on three clinical outcomes (health-related QOL, disease-free survival, and metastasis-free survival). Treatment selection bias is an inherent part of any pragmatic observational study design. To address potential confounding by indication in the comparison of radical cystectomy and those receiving intravesical therapies, we will utilize a novel state-of-the-art method called targeted maximum likelihood estimation (TMLE) as our primary analytic approach.¹³⁻¹⁵ TMLE is an innovative analytic method for causal effect estimation using observational data. Unlike general propensity score-based or G-computation approaches, TMLE is doubly robust to misspecification arising from an omitted confounding variable in the models for the exposure (treatment) or the outcome measure. Unlike approaches that focus on creating carefully matched treatment and control groups, *TMLE allows for the inclusion of all patient participants and their reported outcome measures.*¹³⁻¹⁵

TMLE uses a prediction model such as covariate-adjusted regression to generate an initial estimate of the

treatment effect of radical cystectomy through the creation of *potential outcomes*: two predicted outcomes for each individual patient participant, under the hypothetical assumption that they had been treated with either radical cystectomy or medical management. Next, similar to a propensity score approach, TMLE estimates the probability of treatment with radical cystectomy using either logistic regression, machine learning (LASSO, regression trees, etc.) or super learning approaches.¹⁶ In the third step of the TMLE approach, we use the probabilities obtained in the second step to update the initial estimate of each patient participant's pair of potential outcomes under each treatment group. Specifically, we will generate *targeted* estimates of the potential outcomes with regression models that incorporate both the initial potential outcome estimates and the probability of being treated with radical cystectomy. The average treatment effect is the mean difference between the updated potential outcomes and is interpreted as the causal difference in QOL if all patients had been treated with medical management versus having been treated with radical cystectomy.¹⁶ Because each patient has a pair of potential outcomes under each treatment, subgroup analyses are straightforward. As a secondary sensitivity analysis, we will evaluate these data using propensity score and G-computation methods. As a doubly robust and more efficient analytic approach relative to the comparative secondary approaches, we will use TMLE for presentation of the primary results for this study.

Longitudinal trajectories of the effect of treatment on patient QOL over time will be modeled and characterized using standard linear mixed effects models (primary analysis) or generalized estimating equations (GEE, secondary analysis). We will include covariates in the longitudinal data model to provide treatment effect estimates for subgroups of interest such as those defined by age, comorbidity, caregiver status, tumor severity, and use of investigational agents. For assessment of time-to-event outcomes (e.g., survival), we will use an extension of the TMLE approach appropriate for survival data.¹⁷

In a comparative study using observational data, one perceived threat to validity is that the types of patients who choose radical cystectomy are inherently different demographically or clinically compared with patients who choose medical management. To evaluate this concern, we examined linked SEER-Medicare data for the years 2004-2011 and identified 2,359 patients with recurrent high-grade NMIBC who underwent at least two courses of BCG and compared them with 551 patients with recurrent high-grade NMIBC who underwent radical cystectomy following at least one course of intravesical BCG. These inclusion criteria matched our anticipated CISTO cohort as rigorously as possible with administrative data.

Aim 2 hypotheses concern the effects of patients' preferences at baseline on treatment choice and future quality of life. Preferences and quality of life will be assessed at baseline and at 12 month follow-up using time tradeoff (TTO) questions, in which patients indicate how many years of life they would be willing to "trade off" in order to experience perfect health instead of their current health (to measure quality of life) or one of three negative health outcomes (to measure health preferences): retained bladder and non-metastasized NMIBC, removed bladder and non-metastasized NMIBC, and metastasized bladder cancer. These questions yield a utility score for each health state. Quality of life will also be assessed using the EQ-5D-5L. Hypothesis 2.1 concerns the relationship between treatment choice and patient preferences at baseline for anticipated health conditions in the future. To test this hypothesis, treatment choice will be modeled as a function of patient preferences for future health states while controlling for patients' current health-related QOL, demographic and other characteristics using logistic regression. Hypothesis 2.2 concerns the relationship between changes to experienced health-related QOL from baseline to 12 months post-enrollment and baseline patient preferences for future health states. To test this hypothesis, health-related QOL at 12 months post-enrollment will be modeled as a function of patient preferences while controlling for patients' health-related QOL at baseline, demographic and other characteristics using beta

regression, as described in Basu 2011,¹⁸ stratified by treatment arm. We anticipate that individuals who survive and complete QOL evaluations at 12 months post-treatment may not be representative of all those initially enrolled. We plan to account for this using an inverse probability weighting approach. Both measures of QOL at 12 months post-enrollment (TTO and EQ-5D-5L) will be used in separate models, each with the corresponding measure at baseline included as a covariate.

To identify key themes for Aim 2 patient and caregiver interviews, interview transcripts will be reviewed for accuracy and de-identified before being uploaded into a qualitative analysis program.¹⁹ Members of the research team will review transcripts and independently generate an initial code list. Through an iterative process of coding, discussion, and reconciliation, coding pairs will propose new codes and identify coding patterns. The coding team will summarize emerging themes for the larger team to review and assess thematic saturation as the point at which additional interviews do not yield more information about decision-making and preferences for recurrent high-grade NMIBC that have failed first-line BCG.

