## 1. General Design Considerations

### 1.1 Aims and Hypotheses

**Aim 1:** To compare patient-reported and patient-centered clinical outcomes between patients undergoing radical cystectomy and those receiving bladder-sparing therapies (BST) for NMIBC that have failed first-line BCG.

*Hypothesis 1.1: Patients undergoing radical cystectomy will have worse generic health-related QOL within 12 months of bladder removal surgery compared with BST patients.*

*Hypothesis 1.2: 12-month disease-free survival and metastasis-free survival will be better among radical cystectomy patients than among BST patients.*

*Hypothesis 1.3: Patient-reported and clinical outcome differences will vary within important subgroups including women, non-white patients, elderly patients, patients with multiple comorbid health conditions, patients with poor urinary function scores at the time of BCG failure, patients without caregivers, patients with atypical cancer histologies, and patients receiving investigational agents.*

**Aim 2:** To characterize the heterogeneity of treatments received and corresponding patient and caregiver preferences for NMIBC that have failed first-line BCG.

*Hypothesis 2.1: Patients who choose radical cystectomy for NMIBC with BCG failure will do so more often because they feel this offers their best chance for survival. Patients who choose BST will do so more often because they are concerned about the complications and QOL detriments associated with radical cystectomy.*

*Hypothesis 2.2: Patient and caregiver preferences will correlate strongly with observed treatments received and health-related QOL outcomes. We anticipate that QOL will vary by concordance of treatments received with treatment preferences and health state utilities.*

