## 3. Secondary Outcomes

For patients, secondary outcomes through 12 months include self-reported urinary, bowel, and sexual function and bothersomeness as measured with the Bladder Cancer Index, PROMIS depression and anxiety, EuroQoL 5D, NMIBC treatment preferences, decisional regret, financial distress measured with the Comprehensive Score for Financial Toxicity (COST), healthcare utilization measured as 12-month hospital and urology clinic days, return to work/normal activities, 12-month cancer-specific survival, metastasis-free survival, bladder cancer-specific survival, and progression to muscle-invasive bladder cancer. Among patients with available data, we will assess health-related quality of life, health literacy, urinary function, sexual function, financial distress, healthcare utilization, disease-free and metastasis-free survival, bladder cancer-specific survival, and progression at up to 48 months, and up to 6 additional years for extended follow-up.

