## 4. Data Analyses

We will use descriptive statistics to characterize the treatments received, PROs, and clinical outcomes. Prior to statistical analysis, we will first compare continuous demographic and clinical characteristics by treatment group with Wilcoxon rank-sum tests to protect against violations of normality assumptions. P-values from Exact Conditional Tests, such as Fisher's exact test and its multi-degree of freedom extensions, will be used to compare categorical data.

To address treatment selection bias and potential confounding by indication in the comparison of BST vs. radical cystectomy, we will utilize targeted maximum likelihood estimation (TMLE) as the primary analytic approach for causal effect estimation using observational data. Unlike approaches that focus on creating

carefully matched treatment and control groups, TMLE allows for the inclusion of all patient participants and their reported outcome measures. TMLE first uses covariate-adjusted regression models to generate an initial estimate of the treatment effect of radical cystectomy through the creation of *potential outcomes*: two predicted outcomes for each individual patient participant, under the hypothetical assumption that they had been treated with either radical cystectomy or BST. Next, as with a propensity score approach, we will estimate the probability of treatment with radical cystectomy using SuperLearner. The SuperLearner procedure selects the best weighted combination of prediction models from among candidate learners such as logistic regression, stepwise logistic regression, generalized additive models, Bayesian GLM, LASSO, random forest, gradient descent boosting, support vector machine, and the sample mean. Finally, we will use the probabilities obtained in the second step to update the initial estimate of each patient participant's pair of potential outcomes and the TMLE estimate is interpreted as the difference in outcomes if all patients had been treated with BST versus having been treated with radical cystectomy.

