## 4.2 Secondary Outcomes

Other patient reported outcomes will be evaluated using a similar analytic framework to the primary outcome. To test the hypothesis that cancer-specific survival will be better in patients undergoing radical cystectomy, we will use a superiority testing framework. For assessment of time-to-event outcomes we will use inverse probability weighted Cox proportional hazards models to estimate relative risks. Survival outcomes will be censored at the time of the last study contact or clinic visit for patients who are lost to follow-up and have no recent EHR-verified clinic visits. Since time-to-event outcomes (cancer-specific survival and metastasis-free survival) will be highly correlated with one another, two-sided 95% confidence intervals will be used for inference without adjustment for multiple survival endpoints.

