## 6. Sample Size and Accrual

With recruitment of 572 participants, this study has  $>0.80$  statistical power to detect small differences in QOL between treatment approaches (Cohen's  $d = 0.24$ , or 5.5 points on the physical function scale of EORTC-QLQ-C30). Power analyses conservatively allowed for 10% missing data and assumed a correlation between repeated QOL measurements of 0.3. Assuming a similar balance of treatments within subgroups, this study also has  $>0.80$  power to detect moderate but clinically important treatment effects (Cohen's  $d = 0.43$ , or 9.9 points on the physical function scale of EORTC-QLQ-C30) within subgroups as small as 30% of the study cohort. Anticipated subgroups of this size include patients aged 75 years or older, women, and patients with multiple comorbid health conditions. For the secondary outcome of bladder cancer-specific mortality, data from a review combining multiple trials demonstrated an anticipated 1-year bladder cancer-specific mortality rate of 4.8% when treated with medical management. Assuming a 4.8% mortality rate in the medical management arm, this study has power to detect differences in 1-year bladder cancer-specific mortality rates of  $\leq 1\%$  in the radical cystectomy arm (power  $> 80\%$ ).

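### The protocol and SAP name different main analyses for the time-to-event outcomes, and the SAP's Cox ratio comes without the 12-month risks that Hypothesis 1.2 is about

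*Protocol*

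**What the plan says.** Protocol 9.2 (Analytic Plan) states that for time-to-event outcomes such as survival "we will use an extension of the TMLE approach appropriate for survival data". It prefers TMLE to propensity-score and G-computation methods on the ground that "TMLE is doubly robust to misspecification arising from an omitted confounding variable in the models for the exposure (treatment) or the outcome measure", and it places those other methods in a secondary sensitivity analysis.

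SAP 4 (Data Analyses) also adopts TMLE "as the primary analytic approach for causal effect estimation using observational data". For time-to-event endpoints, however, SAP 4.2 (Secondary Outcomes) says "we will use inverse probability weighted Cox proportional hazards models to estimate relative risks". On censoring it adds, for patients lost to follow-up without a recent verified visit, "Survival outcomes will be censored at the time of the last study contact or clinic visit".

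The question being asked is set elsewhere:

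- Hypothesis 1.2, in SAP 1.1 and in equivalent words in Protocol 3.0: "12-month disease-free survival and metastasis-free survival will be better among radical cystectomy patients than among BST patients".
- SAP 3, in a list introduced as covering outcomes through 12 months: "12-month cancer-specific survival, metastasis-free survival, bladder cancer-specific survival, and progression to muscle-invasive bladder cancer". Disease-free survival is not in that list. It appears only in the next sentence, on follow-up to 48 months and later. Protocol 7.2 does list 12-month disease-free survival.
- SAP 6, on power: "this study has power to detect differences in 1-year bladder cancer-specific mortality rates of" at most 1% under cystectomy, against 4.8% under medical management. Protocol 9.4 uses one-year rates of 0.8% and 3.6% and also gives a two-year power figure.

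**The concern.** There are two separate problems.

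First, the documents give different main analyses for the same outcomes, and neither explains the change or says which takes precedence. With treatment chosen by the patient, the choice of adjustment method can affect the answer, and it should be fixed before results are seen. SAP version 1.0 carries the date of the first data freeze in SAP 1.6 (March 14, 2024).

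Second, the hypothesis and the power statements are framed as survival or risk by a fixed time. A Cox model yields a hazard ratio, which SAP 4.2 calls a relative risk. It becomes a 12-month contrast only with a baseline risk, a horizon and an assumption about the shape of the hazards. SAP 4.2 supplies none of these. It plans no arm-specific 12-month risks, does not repeat the 12-month limit and contains no check of proportional hazards. The trial could therefore report a ratio and still leave open how many more patients in one arm than the other were disease-free at 12 months.

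**Working it through.** **Inputs.** Arm sizes of 235 (cystectomy) and 337 (medical management), and one-year bladder cancer mortality of 0.8% and 3.6%, from Protocol 9.4. One-year rates of 1% and 4.8%, from SAP 6. Recurrence within 12 months of BCG of 24% to 61%, from Protocol 2.1, borrowed only to illustrate an endpoint that is not rare. Two-sided alpha 0.05.

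**1. The plan's own power figure.** SAP 6 states more than 80%. As a comparison of two proportions with unpooled variance:

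- SE = sqrt(0.048 × 0.952/337 + 0.010 × 0.990/235) = 0.0133
- z = 0.038/0.0133 = 2.85
- power = Φ(2.85 − 1.96) = 81.3%

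The arcsine method gives 81.1%. The figure is therefore reproduced as a contrast of one-year proportions, without attrition. Pooled variance gives 73.8% and Fisher's exact test 75.2%. That spread is a separate matter. What counts here is the scale, which is risk at a fixed time.

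**2. Rare endpoint, cut off at 12 months.** Under proportional hazards, 1 − p1 = (1 − p0)^HR, so HR = ln(1 − p1)/ln(1 − p0).

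- HR = ln(0.99)/ln(0.952) = 0.204
- Risk ratio = 0.010/0.048 = 0.208
- Risk difference = 4.8 − 1.0 = 3.8 points

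The two ratios are nearly equal.

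**3. Commoner endpoints, same hazard ratio of 0.204.**

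| Control risk at 12 months | Cystectomy risk, 1 − (1 − p0)^0.204 | Risk ratio | Difference |
|---|---|---|---|
| 4.8% | 1.0% | 0.208 | 3.8 points |
| 24% | 5.45% | 0.227 | 18.6 points |
| 61% | 17.5% | 0.287 | 43.5 points |

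One hazard ratio is compatible with very different 12-month contrasts. The documents give no expected disease-free survival by arm, so these rows show the mechanism and do not predict the result.

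**4. Beyond 12 months.** The 12-month risks were held at 1.0% and 4.8%, each arm was given a Weibull hazard, and the value to which the Cox estimate converges was solved for different lengths of follow-up. The shapes are assumptions.

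| Shapes (cystectomy, medical management) | 12 months | 24 months | 48 months |
|---|---|---|---|
| 1.0, 1.0 (proportional) | 0.204 | 0.204 | 0.204 |
| 0.7, 1.3 | 0.205 | 0.135 | 0.090 |
| 1.3, 0.7 | 0.204 | 0.308 | 0.464 |

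With a 12-month cut-off, non-proportional hazards hardly matter for this rare endpoint. Without one, the ratio depends on follow-up even though the 12-month risks never change.

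**5. Expected bladder cancer deaths at one year.**

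- Protocol rates: 0.008 × 235 = 1.9 and 0.036 × 337 = 12.1
- SAP rates: 0.010 × 235 = 2.4 and 0.048 × 337 = 16.2

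At the SAP rates, one more cystectomy-arm death raises the ratio by about 1/2.35 = 43% but moves the risk difference by only 1/235 = 0.4 points. The chance of no cystectomy-arm death at all is 0.99^235 = 9% (SAP rate) to 0.992^235 = 15% (protocol rate). In that case the hazard ratio has no finite estimate.

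**The case against.** The best defence is that weighted Cox regression is a standard method, that SAP 4.2 is the specific rule and SAP 4 the general one, and that only secondary outcomes are involved. That is fair, and the primary endpoint is untouched. It does not settle which document governs, and it does not supply the 12-month risks.

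A reader might infer more than the documents support:

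- *That the Cox analysis has open-ended follow-up.* SAP 3 introduces these outcomes as running through 12 months and treats longer follow-up separately. SAP 4.2 fails to repeat the horizon, which is a gap in clarity. It does not show that the analysis will be open-ended.
- *That the ratio cannot answer the 12-month question.* For rare bladder cancer death at that horizon it nearly does (step 2).
- *That sparse events require TMLE.* About two deaths in one arm would limit a survival TMLE as well, and a risk ratio would be as fragile as the hazard ratio. The counts also concern bladder cancer death, which is not a Hypothesis 1.2 endpoint. They support reporting absolute risks and do not favour one estimator.
- *That the weights rest on one simple propensity model.* SAP 4 plans SuperLearner for the treatment probabilities, although SAP 4.2 does not say what supplies the weights.
- *That the protocol's method already delivers 12-month risk differences.* Protocol 9.2 gives one sentence and a citation, with no estimand or horizon.

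Proportional hazards is doubtful on judgement. The clock starts at the baseline survey (SAP 1.4), treatment may be delayed (SAP 4.3), and Protocol 9.1 expects as many as a fifth of the medical-management arm to have cystectomy within the year. No figure in the documents shows that hazards will be non-proportional.

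The E-values in SAP 4.4 work on a ratio scale, which favours keeping a ratio. A 12-month risk ratio serves that purpose.

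**Conclusion.** The conflict between Protocol 9.2 and SAP 4.2 is plain and unexplained. As written, SAP 4.2 does not commit to the 12-month quantity that Hypothesis 1.2 names, or to the fixed-time risks behind the power statements. The hypothesis and the power statements share a one-year horizon but not an endpoint: disease-free and metastasis-free survival in the first, bladder cancer-specific mortality in the second.

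The practical size is endpoint-dependent. It is negligible for bladder cancer death cut off at 12 months (0.204 against 0.208). It grows for commoner endpoints (0.204 against 0.287 at an illustrative 61% control risk). Under the assumed Weibull shapes, the hazard ratio ranges from 0.090 to 0.464 at 48 months with the 12-month risks unchanged. The documents do not support the stronger conclusion that weighted Cox is invalid here or that TMLE must replace it. The choice between estimators is a debatable trade-off. Naming one and reporting 12-month risks is not. This should be corrected, as a matter for secondary outcomes.

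**What to change.** 1. Reconcile Protocol 9.2 and SAP 4.2 to one governing method for time-to-event outcomes, and record the date and reason for the change.
2. State the 12-month horizon in SAP 4.2.
3. For each time-to-event outcome, including the disease-free survival named in Hypothesis 1.2, make the main result the confounding-adjusted 12-month risk in each arm and the risk difference with a 95% CI. This can come from survival TMLE, as in the protocol, or from weighted survival curves using the same propensity weights.
4. Keep the weighted Cox model as supportive, call its output a hazard ratio, and add a proportional-hazards check.
5. Compute the SAP 4.4 E-values from the 12-month risk ratio.

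The cost is SAP wording and modest programming, with no new data collection. The downside is that no single hazard ratio serves as the headline. The change does not remove the imprecision that comes from about two expected bladder cancer deaths in the cystectomy arm.
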